Appendix L Q-SAW Substudy

L 1 Substudy Synopsis

Background: A composite endpoint (COPDCompEx) for exacerbations is a novel endpoint that is being used as a surrogate efficacy endpoint for exacerbation risk reduction in randomised controlled trials. COPDCompEx captures AWEs, ie, clinically relevant deteriorations of PEF, reliever use or symptoms that fulfil specific criteria in terms of reaching thresholds or slopes. The Q-SAW substudy aims to provide a deeper understanding of day-to-day variations in symptoms and the impact of AWEs on the participant's life.

Objectives:

- 1 To evaluate the impact of an AWE on daily lives of patients with COPD
- 2 To identify and explain the AWE associated behaviours

Methods: A qualitative substudy will be conducted using a grounded theory approach (Strauss and Corbin 1994). Two semi-structured individual interviews will be conducted by video call or telephone call using open-ended questions, each of 30-minute duration. A topic list and interview guide with example questions will be used as a framework for the interviews (Appendix L 3).

Participant selection: Participants from selected sites in selected countries may be eligible for participation.

Participants who provided informed consent for this substudy may be invited for the initial interview after occurrence of an AWE. Study site personnel and interviewers will be instructed to avoid sharing information on the full study objectives and the procedure by which the participant will be selected for the interview in order not to influence the participant's recognition of having an AWE upon which any follow-up actions would be expected. Instead, participants will be informed that the aim of this substudy is to learn more about the impact of COPD on daily life. A second interview will be scheduled up to 6 weeks after the first interview when most participants are expected to have recovered from the AWE (Wageck et al 2019).

Selection of participants will continue until saturation in topics is achieved, which is expected to occur within a total of approximately 40 participants.

Methods of Analysis: Audio recordings of interviews will be transcribed and analysed with qualitative content analysis. Data will be coded and analysed by 2 researchers and consensus will be reached about potential discrepancies. Results will be systematically discussed with experts in the field. To achieve saturation in interview topics, data collection and coding will be done in an iterative manner. This allows for adaptation of the interview guide based on new

insights. The method of 'constant comparison' will be used for coding thereby expanding an initially defined coding tree (ie, according to the interview guide) with superordinate and subordinate themes.

L 2 Collection of Adverse Events During Participant Interviews

If a participant during the interview reports an AE, which occurred at any time, this will be recorded by the interviewer. For each AE the following variables will be collected:

- Participant details: Patient Ecode, Gender, Age.
- Treatment details: AstraZeneca product, Dose regimen, Date when treatment received.
- AE details: Description of AE (what experience), Date when the AE started and stopped, Whether the AE required any medical intervention (eg, hospitalization, medical treatment etc), Causality, Action taken with regard to medicinal product, Outcome.
- If follow-up is consented by the participant (Yes/No)
- Reporter information (name and contact information)
- Date/time of AE reporting
- Causality collection
- Causality assessment will be done by the participant. The interviewer will ask about causality during the interview ("Do you consider that there is a reasonable possibility that the event may have been caused by drug X?").

L 2.1 Reporting of Adverse Events During the Interviews

Participants will be encouraged to contact the clinical study team when AE or product complaints come up during the interview. The interviewer will ensure that all the necessary information is provided to the PI of the CRESCENDO study site. The PI will prompt GPRI if important or relevant information is missing. Follow-up is undertaken only if the participant has consented to be followed-up. If so, GPRI informs the PI of any follow-up information within the same timeframe as the original report.

In the event that GPRI and its Employees, during the course of performing the Services, become aware of an AE or other reportable safety information with or without an associated AE, (as defined by AstraZeneca's policies and the AE and other safety reporting training program) involving any AstraZeneca Group company product that is the subject of this Agreement, GPRI and its Employees are required to collect and submit within one business day from becoming aware, the appropriate information to AstraZeneca in accordance with AstraZeneca's policies, procedures, and any training provided by AstraZeneca. AstraZeneca is responsible for reporting AEs and other safety information to regulatory and government authorities.

L 3 Topics of Interview Guide

The interviews with participants will be centred around the following topics. Each interview will end with a reflection on discussed issues and potential omissions.

Topics First Interview

Current health status

- Symptoms
- Comorbidities
- Management of COPD
- Impact on daily task / responsibilities
- Impact on relationships with family /friends

Perception of COPD symptoms and exacerbations

- Variation in symptoms
- Understanding the difference between typical and bad days in:
 - Mood
 - Daily activities and tasks
 - Duration relative to one another
 - Participant's perceived reasons

Reflection

Topics second interview

Current health status

- Symptoms
- Comorbidities
- Management of COPD
- Impact on daily task / responsibilities
- Impact on relationships with family /friends

Health behaviour

- Anticipation of exacerbations
- Actions to control exacerbations

Barriers to reaching out

- Personal history with health care (in general)
- Participant's opinion about health care

Reflection

L 4 References

Strauss and Corbin 1994

Strauss A and Corbin J. Grounded Theory Methodology: An Overview. in Handbook of Qualitative Research. 1994;273–285.

Wageck et al 2019

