8.4.2 Follow-up of AEs and SAEs

Any AEs that are unresolved at the participant's last AE assessment in the study are followed up by the investigator for as long as medically indicated, but without further recording in the eCRF. AstraZeneca retains the right to request additional information for any participant with ongoing AE(s)/SAE(s) at the end of the study, if judged necessary.

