8.4.3 Causality Collection

The investigator should assess causal relationship between IMP and each AE, and answer 'yes' or 'no' to the question 'Do you consider that there is a reasonable possibility that the event may have been caused by the IMP?'

For SAEs, causal relationship should also be assessed for other medication and study procedures. Note that for SAEs that could be associated with any study procedure the causal

relationship is implied as 'yes'.

A guide to the interpretation of the causality question is found in Appendix B.

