8.4.8 Reporting of SAEs

All SAEs must be reported, whether or not considered causally related to the IMP. All SAEs will be recorded in the eCRF.

If any SAE occurs during the study, investigators or other site personnel will inform the appropriate AstraZeneca representatives within one day ie, immediately but **no later than 24 hours** of when he or she becomes aware of it.

The designated AstraZeneca representative will work with the investigator to ensure that all the necessary information is provided to the AstraZeneca Patient Safety data entry site within one calendar day of initial receipt for fatal and life-threatening events and within 5 calendar days of initial receipt for all other SAEs.

For fatal or life-threatening AEs where important or relevant information is missing, active follow-up will be undertaken immediately. Investigators or other site personnel will inform AstraZeneca representatives of any follow-up information on a previously reported SAE within one calendar day, ie, immediately but **no later than 24 hours** of when he or she becomes aware of it.

Once the investigators or other site personnel indicate an AE is serious in the eCRF, an automated email alert is sent to the designated AstraZeneca representative.

If the eCRF is not available, then the investigator or other study site staff reports the SAE via secure method to the appropriate AstraZeneca representative.

When the eCRF is temporarily not accessible, the AstraZeneca Study Representative should confirm that the investigator/site staff enters the SAE in the AstraZeneca eCRF when access resumes.

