Appendix N Patient Experience Interview Substudy

N 1 Synopsis

Background and Objectives: This substudy has two aims. First, to get more in-depth insight into the perceptions and experiences of participants on this study. This substudy complements the data of the quantitative SPFQ (Appendix M) and will be used to understand how participant experience can be improved in this study and in future studies. Secondly, it aims to gain further insight into the participant perceptions and experiences of the digital technology used in the study, including virtual spirometry.

Methods: Approximately 20 participants from selected sites will be invited to take part in a remote, semi-structured interview conducted over video call or telephone call. Overlap with Q-SAW substudy sites or participants will be avoided. The duration of the remote, semi-structured interview will be approximately 60 minutes. The timepoints of the interviews will be stratified over the study duration, starting after at least 2 study visits.

Methods of Analysis: The interviews will be recorded, transcribed, translated if applicable, and analysed with qualitative content analysis.

Please see Appendix L 2.1 for Adverse Event Reporting requirements for this substudy.

N 2 Interview Guide Themes

CRESCENDO-specific themes / topics			
Themes	Example topics for each theme		
Spirometry / FEV1	Usability/ease of use of virtual spirometry device		
	Experience connecting the device		
	 The overall experience of virtual versus face-to-face spirometry 		
	 Acceptability of this data collection method 		
	Acceptability of time taken to collect data		
Digital patient solutions	Unify usability/ease of use		
	• Unify perceived value as a whole and perceived value of the specific features (e.g., notifications/reminders)		
	Attitude of using provisioned device versus using your own device		
	Acceptability of time taken to collect data		
	ePRO completion via smartphone (daily diary)		
Visits	Experience of preparing for and attending a		
	 face-to-face visit 		
	o virtual visit		
	Perceived value of a		
	o face-to-face visit		
	o virtual visit		
	Attitudes and perceptions related to communication, comfort, trust		
Non-financial impact	Expected and actual time commitment		
	Impact on usual daily activities (eg work)		
	Impact on level of energy		
	Overall satisfaction		
Motivation to	What motivated the participant to enter the study?		

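### Appendix L 2.1, which Appendix N adopts, gives the interview vendor one business day to report any adverse event and sets no time limit for telling the site, so an SAE heard on a Friday can reach the sponsor 72 hours or more later, against 24 hours in Section 8.4.8

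*Protocol*

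**What the plan says.** **Interview substudies.**
- Timing to the sponsor: Appendix L 2.1 says the vendor and its staff "are required to collect and submit within one business day from becoming aware". This covers every AE, and no shorter period is given for serious ones.
- Timing to the site: the interviewer must see that the site investigator receives the information. No time limit is given.
- Follow-up: the investigator may prompt the vendor for missing information. The next sentence is "Follow-up is undertaken only if the participant has consented to be followed-up". If consent was given, the vendor passes any follow-up information to the investigator in the same timeframe as the original report.
- Causality: Appendix L 2 says "Causality assessment will be done by the participant", using the same reasonable-possibility question that Section 8.4.3 puts to the investigator.
- Scope: Appendix N says "Please see Appendix L 2.1 for Adverse Event Reporting requirements for this substudy". It cites L 2.1 and not L 2.

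**Main protocol.**
- Section 8.4.8: for an SAE, "investigators or other site personnel will inform the appropriate AstraZeneca representatives within one day ie, immediately but" no later than 24 hours after learning of it. Where key information on a fatal or life-threatening event is missing, it is pursued at once.
- Section 8.4.3: "The investigator should assess causal relationship between IMP and each AE".
- Section 8.4.2: "Any AEs that are unresolved at the participant's last AE assessment in the study are followed" up by the investigator while there is a medical need.
- Section 7.1: after permanent discontinuation of treatment, AE follow-up ends on withdrawal of consent to the study, loss to follow-up or entry into another study. Refusal for a single event is not on that list.

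**The concern.** The interviewees are randomised participants in a blinded trial, so Section 8.4 governs their adverse events. Q-SAW invites people to the first interview after an acute worsening, and the interviewer records whether an event led to hospitalisation. SAEs are therefore a foreseeable product of these interviews.

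An interviewer may be the first person connected with the trial to hear of an event. From that point the appendix uses a slower clock to the sponsor than the main protocol uses for SAEs, and no clock to the site. Section 8.4 uses 24 hours not only for SAEs but also for pregnancy (8.4.10.1), medication error, abuse and misuse (8.4.11.1) and overdose (8.4.12). The business-day limit stands alone.

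What is at stake is prompt knowledge of serious events. Sections 7.1.1 and 7.1.2 make decisions about study treatment depend on the site learning of rash and serious infection. No efficacy analysis or sample-size figure is affected.

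**Working it through.** There is no figure in the plan to reproduce. The check is calendar arithmetic on the vendor-to-sponsor limit, then a reading of the other steps side by side.

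**Timing to the sponsor.** Assumptions, since the protocol does not define a business day: business days run Monday to Friday, and the vendor learns of the event at 09:00. The deadline is read in two ways: the same clock time on the next business day, or midnight at the end of that day. The second reading adds 24 − 9 = 15 hours. Permitted time = deadline minus time of awareness. For a Friday this is 3 × 24 = 72 h, or 72 + 15 = 87 h. With a Monday holiday it is 4 × 24 = 96 h, or 96 + 15 = 111 h.

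| Vendor learns of event | Same clock time | End of day | Excess over 24 h |
|---|---|---|---|
| Monday to Thursday | 24 h | 39 h | 0 to 15 h |
| Friday | 72 h | 87 h | 48 to 63 h |
| Saturday | 48 h | 63 h | 24 to 39 h |
| Sunday | 24 h | 39 h | 0 to 15 h |
| Friday before a Monday holiday | 96 h | 111 h | 72 to 87 h |

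**Timing to the site.** L 2.1 states no limit, so this delay cannot be bounded. The phrase about follow-up information using the original report's timeframe does not help, because no timeframe to the investigator is given. If one took the business-day limit to cover that step too, the same table would apply.

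**Follow-up.** The consent sentence stands between the investigator prompting the vendor and the vendor informing the investigator. In that position it reads most naturally as limiting the vendor's re-contact of the interviewee. The text does not say so, and it makes no exception for SAEs, although Section 8.4.8 requires immediate pursuit of missing information on fatal or life-threatening events.

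**Causality.** L 2 gives the assessment to the participant and Section 8.4.3 gives it to the investigator for each AE. L 2 neither says that the participant's answer replaces the investigator's nor that the investigator's is still required.

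**Who is covered.** About 40 in Q-SAW (Section 4.1.2) plus about 20 in the experience interviews (Appendix N) gives 60, and 60/406 = 14.8% of those to be randomised. Appendix N says overlap between the two is avoided, so the sum is fair. The ceiling on interviews is 40 × 2 + 20 = 100. It is a ceiling because Q-SAW participants may be invited to two interviews and need not have both.

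**The case against.** The strongest reply is that the two timing rules bind different parties. The 24 hours in Section 8.4.8 bind investigators and site personnel, for SAEs. The business day binds the vendor, for any AE. The investigator's own 24 hours still start once the investigator is aware, and Section 8.4.8 sets no 24-hour limit for non-serious events. This stands: site staff are not told to break their rule. It does not close the gap, because an SAE known only to the vendor can wait over a weekend.

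Safeguards also exist. Section 7.1.2 has participants told at each visit to stop study treatment and contact the investigator at once about a rash, and L 2.1 has interviewees encouraged to contact the study team. The interview adds a route of detection and removes none. These safeguards stand too, but they rely on the participant and not on the person who has just heard of the event.

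The vendor's agreement and the sponsor's safety training, both mentioned in L 2.1, may hold a shorter limit for SAEs. They cannot be seen here, and the protocol text does not refer to such a limit.

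A reader might infer more than the documents support:
- That events heard in interviews go unfollowed. L 2.1 routes them to the investigator, and nothing suspends Sections 7.1, 8.4.2 or 8.4.9.
- That the weekend delay can be turned into a number of extra doses before the site hears. The business-day clock runs to the sponsor, and the step to the site has no stated length.
- That the SAP's relatedness tables would be contaminated. They use the investigator's assessment (SAP 4.7.2.2), and nothing feeds the participant's answer into them.
- That participants assess causality in both substudies. Appendix N adopts only L 2.1, and the causality sentence is in L 2.

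**Conclusion.** The point holds as a gap in safety reporting that needs reconciling. Under the stated vendor rule an SAE heard on a Friday may reach the sponsor after 72 to 87 hours, or 96 to 111 hours with a Monday holiday, and the hand-over to the investigator has no limit at all. These figures rest on a Monday-to-Friday working week, awareness at 09:00 and the two readings of the deadline. On an ordinary weekday the excess over 24 hours is 0 to 15 hours.

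The consent condition and, for Q-SAW only, the causality sentence are ambiguous beside Section 8.4. They do not override it. The 60 participants are planned interviewees, not people shown to be harmed: a delay would need an event not already reported, told to an interviewer, by someone who does not also contact the site. The change is worth making because it is small and brings the appendix into line with the protocol's own limit.

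**What to change.** Reconcile Appendix L 2, L 2.1 and the cross-reference in Appendix N with Sections 7.1, 8.4.2, 8.4.3 and 8.4.8:

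- Apply the protocol's existing limit (immediately, and no later than 24 hours after becoming aware, weekends and holidays included) to the vendor's SAE reports to the sponsor and to the interviewer's hand-over to the investigator.
- State that Section 8.4 applies in full to events heard in interviews, and that the consent condition limits only the vendor's re-contact of the interviewee.
- State in L 2 that the investigator assesses causality under Section 8.4.3 and that the participant's answer is supplementary information.

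The cost is a wording change in the appendices and matching vendor instructions. Weekend reporting may also need a small change to the vendor's contract. No new data are collected and no analysis changes.

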Appendix M SPFQ Substudy

M 1 Study Synopsis

This study will include an option for participants to complete a questionnaire, the SPFO, which will give participants the opportunity to provide feedback on their clinical study experience. Participants will be asked to complete the questionnaire at the beginning, middle and end of the study in electronic format. Individual participant level responses will be anonymous to the investigator and site staff and so will not be reviewed by investigators. Coded responses will be used by the sponsor to understand participant experience on clinical studies and to identify where improvements can be made in the clinical study process. To do this, responses will be combined across studies and with data collected as part of the study, such as gender, ethnicity, and trial duration, to investigate correlations with the participant experience. Aggregated data may be shared, maintaining individuals' anonymity, with site staff so they can take steps to understand and improve the participant experience at their site. Data may also be compared with responses from other research partners/sponsors to better understand participant experience in clinical studies across the biopharmaceutical industry. This questionnaire does not collect data about the participant's disease, symptoms, treatment effect or adverse events and therefore would not be study data. Consequently, these data do not contribute to any endpoints on the study and will be analysed and reported separately from the clinical study data. The results of this participant experience analysis may be published or presented at scientific meetings, with the sponsor complying with the requirements for publication.

M 2 Study Participant Feedback Questionnaire

Patient Experience Initiative

Study Participant Feedback Questionnaire (SPFQ)

Version 1.0

Prepared by:

TransCelerate Patient Experience Initiative Team

This deliverable prepared by TransCelerate BioPharma can be adopted by member companies and others, but all adoption is purely voluntary and based solely on the particular company's unilateral decision. TransCelerate has provided this Study Participant Feedback Questionnaire ("SPFQ") and the corresponding User Guide (collectively the "Work Product") for informational purposes only. By using the Work Product, you manifest your assent to the terms of use set out in this paragraph. The Work Product are not tailored to any particular factual situation and are provided 'AS IS' WITHOUT WARRANTY OF ANY KIND, EITHER EXPRESSED OR IMPLIED, INCLUDING, BUT NOT LIMITED TO, THE IMPLIED WARRANTIES OF FITNESS FOR A PARTICULAR PURPOSE, NON-INFRINGEMENT, OR MERCHANTABILITY. TransCelerate and its members do not accept any responsibility for any loss of

any kind including loss of revenue, business, anticipated savings or profits, loss of goodwill or data, or for any indirect or consequential loss whatsoever to any person using the Work Product. Any party using the Work Product bears sole and complete responsibility for ensuring that the Work Product, whether modified or not, are suitable for the particular clinical trial, accurate, current, commercially reasonable under the circumstances, and comply with all applicable laws and regulations.

Section A: Your experience before you started the study <to be completed within 1 month of study enrollment>

Thank you for your participation. Your experiences in this trial are important to us and we would like to hear about them. Your answers will help us improve future trials. There are no right or wrong answers, and it will take approximately 5 minutes to complete. Your answers will be kept anonymous and will not impact your participation in this trial.

Please select one response for each item.

- I understand the treatment process in this trial (for example: when and how to take or use a treatment)
- The information given to me before I joined the trial was everything I wanted to know (for example: visits and procedures, time commitment, who to contact with questions)
- The information given to me before I joined the trial was easy for me to understand (for example: visits and procedures, time commitment, who to contact with questions)
- I felt comfortable that I could ask any questions before I joined the trial

Strongly disagree	Disagree	Neither agree or disagree	Agree	Strongly Agree
0	1	2	3	4

Section B: Your experience during the trial <to be completed during trial progress>

Thank you for your participation. Your experiences in this trial are important to us and we would like to hear about them. Your answers will help us improve future trials. There are no right or wrong answers, and it will take approximately 5 minutes to complete. Your answers will be kept anonymous and will not impact your participation in this trial.

Please select one response for each item.	Strongly disagree	Disagree	Neither agree or disagree	Agree	Strongly Agree
1 . Overall I am satisfied with the trial site (for example: comfort and privacy of treatment area, waiting area, parking, ease of access to the site)	0	1	2	3	4
2 . My trial visits have been well organized					
$\boldsymbol{3}$. My trial visits are scheduled at a convenient time for me					
4 . The staff treats me with respect					
${\bf 5}$. I feel comfortable that I can ask questions during the trial					
6 . I am satisfied with the answers I have received to my questions during the trial					
1	No		Yes	'	-
7 . The time taken to collect data is acceptable to me (for example: in person visits, questionnaires, forms)					
8 . The impact the trial has on my daily activities is acceptable (for example: household chores, work commitments, eating)					

Section C: Your experience at the end of the trial <to be completed at last trial visit>

Thank you for your participation. Your experiences in this trial are important to us and we would like to hear about them. Your answers will help us improve future trials. There are no right or wrong answers, and it will take approximately 5 minutes to complete. Your answers will be kept anonymous and will not impact your participation in this trial.

Please select one response for each item.	No		Yes		
$\boldsymbol{1}$. I was informed when I had completed the trial					
$2 \ \Box$ I was informed of any future opportunities to access the overall trial results if I wanted to					
	Strongly disagree	Disagree	Neither agree or disagree	Agree	Strongly Agree
3 . Overall, I was satisfied with the information I received about future support after the trial (for example: future treatment, follow-up contact details)	0	1	2	3	4
4 . Overall, I was satisfied with my trial experience					
-	Much less than expected	Somewhat less than expected	Same as expected	Somewhat more than expected	Much mor than expected
5 ; Compared to when the trial started, the overall commitment required was similar to what I expected	0	1	2	3	4

